 - Patients who are thought by the hepatic surgeon to be suboptimally resectable are included. This will normally include patients, for instance, who have potentially resectable disease but in whom compromise of the resection margins is likely. These patients are currently normally treated with pre-operative chemotherapy under NICE guidance. This decision will be at the surgeons discretion.
 - Unidimensionally measurable disease (RECIST criteria, see AAppendix V) to measure pre-operative response.
 - Patients with previously resected liver metastases for whom surgery was performed ≥ 1 year previously.
 - No previous systemic chemotherapy for metastatic disease.
 - adjuvant chemotherapy with 5FU +/- FA, Capecitabine or Oxaliplatin may have been given, if completed > 6 months prior to trial entry.
 - rectal chemoradiotherapy with 5FU +/- FA may have been given, if completed > 1 month prior to trial entry.
- WHO performance status (PS) 0, 1 or 2 (see AAppendix VII) and considered by responsible consultant to be fit to undergo combination chemotherapy.
 - Baseline laboratory tests (within 1 week prior to randomisation):
 - neutrophils $\geq 1.5 \times 10^9/l$ and platelet count $\geq 100 \times 10^9/l$
 - serum bilirubin $\leq 1.25 \times$ upper limit of normal (ULN), alkaline phosphatase $\leq 5 \times$ ULN, and serum transaminase (either AST or ALT) $\leq 2.5 \times$ ULN
 - estimated creatinine clearance (Cockcroft; Appendix VIII) >50 ml/min or measured GFR (EDTA clearance) >50 ml/min.
 - All patients must be aged 18 years or older.
 - For women of childbearing potential, negative pregnancy test and adequate contraceptive precautions. Adequate contraception for men.
 - Written informed consent.
 - Consent to allow surplus pathological material to be analysed for translational research projects (*patients may decline participation in this supplementary component and still participate in the main trial*).

Exclusion criteria

- Patients who are unfit for the chemotherapy regimens in this protocol, e.g.:
 - severe uncontrolled concurrent medical illness (including poorly-controlled angina or very recent MI, i.e. in previous 3 months) likely to interfere with protocol treatments.
 - Any psychiatric or neurological condition which is felt likely to compromise the patient's ability to give informed consent or to comply with oral medication.
 - Partial or complete bowel obstruction.
 - Pre-existing neuropathy (> grade 1).

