11.e Every chemotherapy cycle (day 1, or up to 3 working days before)

1. Clinical evaluation (doctor/nurse), to include NCI toxicity scores from previous cycle (see Appendix XI) and current WHO PS (see Appendix VII)
2. Check FBC, U&Es, and LFTs (see regimen details in Appendix I for critical values).
3. Measure and record magnesium levels.
4. Recalculate drug doses if patients' weight has changed by more than 10%, or follow local policy.
5. Record Cetuximab administration details for patients in Arm B.
6. These data should be collated on the **Treatment Form** which is returned to UoSCTU every 6 weeks (i.e. after every 3 cycles of OxMdG or IrMdG)

Patients should also complete QoL questionnaires during both pre- and post-operative chemotherapy at the beginning of cycle 4 with OxMdG and IrMdG.

11.f Surgery

Surgical data will be recorded on the surgery form and returned to UoSCTU within four weeks of the date of surgery. Investigators should make local arrangements to ensure that facilities to snap-freeze samples are available during surgery (if possible). Pathology samples (normal and tumour tissue) obtained following liver resection surgery should be requested and sent to the Cancer Sciences Tissue Bank, Southampton (see section 11c) for those patients who have given consent.

11.g After the end of treatment

After completion of study treatment patients will be followed up with the following tests and procedures every 3 months for 2 years, and every 6 months thereafter until progression for a further 3 years and/or death, using the **Progress report & follow-up form**:

1. Clinical examination.
2. Chest, abdomen and pelvis CT scan (or equivalent imaging). Chest x-ray only to be performed if chest CT not available.
3. A QoL form should also be completed every 3 months for the first year and every 6 months thereafter.
4. Magnesium levels should be measured 6-8 weeks after the last dose of Cetuximab and at intervals until hypomagnesaemia has resolved.
5. Documentation of survival status and further anticancer treatments will be done. All deaths should be reported to UoSCTU using the Death CRF.

Patients who progress whilst in follow-up should come off protocol follow-up but treatment and care outcome data should still be collected. The follow-up only form should be completed at the same study time points.

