- FBC and clinical assessment (NCI toxicity scores) should be performed on the day of starting each cycle (or within 3 working days before) and the results available before starting.
- Biochemistry (including creatinine, bilirubin, magnesium and either AST or ALT) is done at the same time as FBC.
- If patient is clinically jaundiced, bilirubin level must be reviewed prior to administration of Oxaliplatin.
- If patient has symptoms of possible hypomagnesemia, check magnesium level and correct as advised (see Appendix XIII).

Toxicity and dose adjustments for OxMdG**Haematological**

- Myelotoxicity occurred in 30% of patients treated with OxMdG in the FOCUS trial.
- Check FBC on (or up to 3 working days before) day 1 of each cycle. Delay 1 week if neutrophils $< 1.5 \times 10^9/l$ or platelets $< 75 \times 10^9/l$. Only treat when neutrophils and platelets are above these limits. The lower limit for the day 1 platelet count for this regimen is due to the possible occurrence of mild thrombocytopenia after a number of cycles of OxMdG.
- If >1 delay, or 1 delay of ≥ 2 weeks occurs, maintain Oxaliplatin and infusional 5FU doses but omit bolus 5FU and continue without bolus 5FU for subsequent doses.
- If a further delay(s) for myelotoxicity occurs despite omitting bolus 5FU reduce the Oxaliplatin and infusional 5FU doses by 20%.
- Further dose reductions may be made, at the discretion of the treating investigator.

Neurotoxicity

- Oxaliplatin commonly causes peripheral sensory symptoms, easily distinguishable from 5FU neurotoxicity, which is uncommon, and cerebellar.
- Many patients experience transient paraesthesia of hands and feet, and some experience dysaesthesia in the throat. These symptoms are precipitated by cold and last from a few hours to a few days after each Oxaliplatin administration. They do not require treatment or dose reduction.
- If symptoms persist until the next cycle is due, and are associated with significant discomfort or loss of function (e.g. dropping objects), omit Oxaliplatin from the regimen and continue with MdG alone. Infusional 5FU should be increased from $2400\text{mg}/\text{m}^2$ to $2800\text{mg}/\text{m}^2$ during this time (any prior 5FU dose reductions should be taken into account). When symptoms have resolved to grade 1, Oxaliplatin should be restarted at the reduced dose of $75\text{mg}/\text{m}^2$ (infusional 5FU should return to normal).

Renal function (see also Appendix IV)

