- If acute hypersensitivity occurs, discontinue the infusion and treat with IV corticosteroid and antihistamine.
- After full recovery, the patient may continue with FA and 5FU.
- At the investigator's discretion, the patient may be rechallenged with Oxaliplatin at the next cycle. In this case, premedication is recommended as follows:
Dexamethasone 4mg p.o. 6 hourly starting 24 hours pre-treatment, + 8mg IV 30 minutes pre-dose
CChlorphenamine 10mg (or equivalent) + Ranitidine 50mg (or equivalent) IV 30 minutes pre-dose. Continue Dexamethasone, CChlorphenamine and Ranitidine for 24-48 hours after treatment with Oxaliplatin.

The IrMdG regimen (IrMdG)

Treatment is given in two-weekly schedules as follows:

Day 1 of treatment schedule (14 day cycle)

0:00	IV bolus Granisetron 3 mg (or equivalent) IV bolus Dexamethasone 8 mg Flush line with 5% Dextrose
0:00-0:30	Irinotecan 180 mg/m ² IV infusion over 30 minutes in 250 ml normal saline
0:30-2:30	l -folinic acid (175 mg flat dose) or d,l -folinic acid (350 mg flat dose) IV infusion, 2 hrs, 250 ml 5% Dextrose Flush line with 5% Dextrose
2:30-2:35	5-Fluorouracil 400 mg/m ² IV bolus over 5 minutes
2:35-48:30	5-Fluorouracil 2400 mg/m ² IV infusion over 46 hours
48:30	Disconnect pump and flush line (5 ml heparinised saline).
Days 4-14	No treatment

Notes:

- Bolus 5FU is recommended to be given over 5 minutes but may be administered as a 15 or 30 minute infusion where this reflects local practice.
- Do not use injection equipment containing aluminium.
- The use of pre-packed 'minibags' of 5FU is acceptable.
- Please check with the UoSCTU if your local policy for pre-chemotherapy medication differs to that stated here to confirm if it is acceptable for use in the trial.

Oral antiemetics (starting day 2):

- Dexamethasone 4 mg tds x 1 day; 4 mg bd x 1 day; 4 mg od x 1 day.
- Domperidone or metoclopramide prn.
- Ensure patient has supplies of Loperamide and Ciprofloxacin, and knows how to use them.

Note on the use of dexamethasone

- For patients at high risk of steroid side effects (e.g. diabetics) or for those who develop toxicity attributable to steroids (e.g. dyspepsia; dysphoria; etc), the oral steroid should be omitted.

Scheduled tests

- FBC and clinical assessment (NCI toxicity scores) should be performed on the day of starting each cycle (or within 3 working days before) and the results available before starting.

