- Biochemistry (including creatinine, bilirubin, magnesium and either AST or ALT) is done at the same time as FBC.
- If patient has symptoms of possible hypomagnesemia, check magnesium level and correct as advised (see Appendix XIII).

Toxicity and dose adjustments for IrMdG**Acute cholinergic syndrome**

- Irinotecan may provoke an acute cholinergic syndrome with diarrhoea, sweating, salivation, bradycardia, etc. This may start during the drug infusion or shortly after.
- If this occurs, give atropine sulphate 0.25 mg s/c immediately. Atropine should then be given prophylactically with subsequent cycles.

Haematological

- Myelotoxicity is commoner with IrMdG than with MdG.
- Check FBC on (or up to 3 working days before) day 1 of each cycle. Delay 1 week if WBC $< 3.0 \times 10^9/l$, granulocytes $< 1.5 \times 10^9/l$ or platelets $< 100 \times 10^9/l$. Only treat when WBC and platelets are above these limits.
- If >1 delay, or 1 delay of ≥ 2 weeks occurs, reduce the Irinotecan and 5FU (bolus and infusion) doses by 20% and continue at the lower dose for subsequent cycles unless further toxicity occurs.
- If a further delay(s) for myelotoxicity occurs despite a 20% dose reduction, a further dose reduction may be made, at the discretion of the treating clinician.

Neurotoxicity

- Neurotoxicity (cerebellar) is uncommon; consider changing to alternative treatment.
- Changes in treatment should be discussed with one of the clinical coordinators.

Renal function (see also Appendix IV)

- Check serum creatinine at each cycle. If this rises $>25\%$, re-check EDTA clearance or 24-hour urinary clearance, and adjust Irinotecan and 5FU doses according to the table in Appendix IV.
- Patients with moderate renal impairment may receive irinotecan, but if GFR $<30ml/min$, the Irinotecan dose should be reduced by 50% and the 5FU dose should be reduced by 25% (see Appendix IV).

Hepatobiliary function (see also Appendix IV)

- Irinotecan and its metabolites are cleared by biliary excretion and patients with cholestasis have delayed clearance.
- LFTs should be checked before each treatment cycle. Patients with serum ALP $>5 \times ULN$ or serum bilirubin in the range $1.5-3 \times ULN$ require a 50% dose reduction of irinotecan;

patients with serum bilirubin >3 x ULN should not receive Irinotecan (please refer to Appendix IV).

- 5FU should be reduced by 50% in patients with serum bilirubin >3 x ULN (see Appendix IV).

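### In both irinotecan regimens the restart sentence of the day-1 blood count rule leaves out granulocytes, one of the three counts that delay a cycle: a minor patient-safety wording correction

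*Protocol*

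**What the plan says.** The haematological rules sit in Appendix I, under the toxicity and dose adjustments for each of the four regimens.

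- **IrMdG and IrMdG plus cetuximab.** The full blood count is checked on day 1 of each cycle or up to three working days before. The delay sentence is "Delay 1 week if WBC $< 3.0 \times 10^9/l$, granulocytes $< 1.5 \times 10^9/l$ or platelets $< 100 \times 10^9/l". The restart sentence directly after it is "Only treat when WBC and platelets are above these limits". The wording is the same in both regimens.
- **OxMdG and OxMdG plus cetuximab.** The delay triggers are neutrophils below 1.5 and platelets below 75 x 10^9/l. The restart sentence is "Only treat when neutrophils and platelets are above these limits".

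Two other places bear on how the rule is used. Section 11.e tells sites, at every cycle, "Check FBC, U&Es, and LFTs (see regimen details in Appendix I for critical values", so Appendix I is the operative source. Under scheduled tests, each irinotecan regimen states that the blood count "should be performed on the day of starting each cycle (or within 3 working days before) and the results available before starting".

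**The concern.** A rule that stops treatment for any of three counts should name all three when it says treatment may go ahead. Here the restart sentence drops one, and the protocol gives no reason. The oxaliplatin regimens, built on the same template, drop none, so this looks like an oversight.

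At stake is a patient whose cycle was delayed and whose white cells and platelets have recovered but whose granulocytes have not. Staff who look only at the restart sentence at the re-check would find both named conditions met and could give irinotecan and 5FU with granulocytes still below the limit that may have caused the delay. Appendix I itself says that myelotoxicity is commoner with IrMdG than with MdG alone. It also suggests that investigators copy the relevant schedule into the patient's notes, so this wording may be what is read at the bedside.

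**Working it through.** The plan states no figure to reproduce. The check is a comparison of the delay and restart sentences, followed by one illustrative case.

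**1. Counts named in each rule (Appendix I, haematological toxicity)**

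| Regimen | Delay triggers (x 10^9/l) | Counts in restart sentence | Named / triggers |
|---|---|---|---|
| OxMdG | neutrophils < 1.5, platelets < 75 | neutrophils, platelets | 2 / 2 |
| OxMdG plus cetuximab | neutrophils < 1.5, platelets < 75 | neutrophils, platelets | 2 / 2 |
| IrMdG | WBC < 3.0, granulocytes < 1.5, platelets < 100 | WBC, platelets | 2 / 3 |
| IrMdG plus cetuximab | WBC < 3.0, granulocytes < 1.5, platelets < 100 | WBC, platelets | 2 / 3 |

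**2. Does the white cell limit cover the missing count?** It does not. The share of white cells that are granulocytes at the 1.5 limit is 1.5 / WBC:

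- at WBC 3.0: 1.5 / 3.0 = 50%
- at WBC 4.0: 1.5 / 4.0 = 37.5%

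A patient just above the white cell limit with a granulocyte share under about 50% satisfies the white cell condition while failing the granulocyte one. At WBC 4.0 the share must be under 37.5%.

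**3. Illustrative re-check (assumed counts, not from the protocol).** WBC 3.4, granulocytes 1.2, platelets 150 x 10^9/l.

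- Restart sentence alone: 3.4 > 3.0 and 150 > 100, so both named conditions are met.
- Delay sentence: 1.2 < 1.5, so delay.
- Granulocyte share: 1.2 / 3.4 = 35.3%.
- If neutrophils are taken as equal to granulocytes, 1.2 is grade 2 in Appendix XI (1.0 to 1.4).

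**4. Does another place complete the restart sentence?** None was found. Section 11.e refers back to Appendix I. Section 9.a asks for bone marrow function to be monitored and points to Appendix IV for dose adjustment, but the tables there cover only renal and hepatic function. The only day-1 granulocyte limit for irinotecan is in the delay sentence itself.

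**5. Do the two sentences conflict?** They do not. The delay rule is tied to day 1 of each cycle. A delayed cycle has not yet started, so the day it starts is its day 1, and a blood count result must be available beforehand. The rule also provides for a single delay of two weeks or more, so it foresees a one-week delay being extended. Read as a whole, it still holds the patient in step 3.

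**The case against.** The strongest reply is that the restart sentence states a necessary condition. It says when treatment may not go ahead; it does not say that two adequate counts are enough, and it does not cancel the delay sentence just before it in the same bullet. With the day-1 check and the required blood count result, a careful reader delays the illustrative patient at the first check and again at the re-check. White cells include granulocytes, so the shorter wording may have been meant to cover both. Section 9.a also makes the treating consultant responsible for following the regimens and directs doubtful dose modifications to the trials unit.

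Most of this stands, and it sets the limit of the point. A reader might infer that the protocol contradicts itself, or that it authorises irinotecan with granulocytes below 1.5. The documents do not support either reading, because the delay sentence applies again whenever the cycle is due to start. A reader might also look to the entry limits in Section 8 for support. They do not help: day-1 limits are not tied to entry limits, since entry requires platelets of at least 100 while the oxaliplatin delay limit is 75.

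What the reply does not remove is the gap in the wording. The sentence that tells staff when to treat lists fewer counts than the sentence that told them to stop, in two regimens out of four.

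**Conclusion.** The point holds as an incomplete restart rule in the two irinotecan regimens. It is a minor patient-safety correction.

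It affects two sentences. In practice it matters only when three things coincide: an irinotecan cycle has already been delayed; the re-check shows white cells above 3.0 and platelets above 100 but granulocytes below 1.5 x 10^9/l; and the person deciding reads the restart sentence without re-applying the delay sentence. The protocol gives no frequency for this, and none is assumed here.

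A knock-on effect on dose is possible but hypothetical. A single delay of two weeks or more calls for a 20% reduction of irinotecan and 5FU, so a patient released after one week with low granulocytes could miss that reduction.

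The wording is identical in both arms. It has no effect on sample size or analysis, and nothing here suggests bias between arms. Section 14 expected recruitment to finish at the end of December 2012, so the practical benefit depends on irinotecan still being given under this text or on the text being reused.

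**What to change.** In the haematological rules for IrMdG and for IrMdG plus cetuximab, add the missing count so that the restart sentence reads: *Only treat when WBC, granulocytes and platelets are above these limits.* Nothing else is needed for this point.

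The cost is one word in two places. No extra test is required, because the full blood count is already taken before every cycle. The only downside is that an occasional irinotecan cycle may be held longer or dose-reduced, which the delay rule already intends.

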Appendix I – Chemotherapy regimens

Regimen	Arm using regimen	Page
OxMdG (Oxaliplatin + MdG schedule)	A	42
IrMdG (Irinotecan + MdG schedule)	A	45
OxMdG + Cetuximab	B	49
IrMdG + Cetuximab	B	58

Investigators may find it helpful to copy the relevant schedule from this Appendix and keep it with the patients' notes.

The OxMdG regimen

Treatment is given in two-weekly schedules as follows:

Day 1 of treatment schedule (14 day cycle)

0:00	IV bolus GGranisetron 3 mg (or equivalent) IV bolus DDexamethasone 8 mg Flush line with 5% DDextrose
0:00-2:00	l -folinic acid (175 mg flat dose) or d,l -folinic acid (350 mg flat dose) IV infusion, 2 hrs, 250 ml 5% Dextrose concurrently with:
0.00-2:00	Oxaliplatin 85 mg/m ² IV infusion, 2 hrs, 250 ml 5% DDextrose
2:00	Flush line with 5% DDextrose again
2:00-2:05	5-Fluorouracil 400 mg/m ² IV bolus over 5 minutes
2:05-48:00	5-Fluorouracil 2400 mg/m ² IV infusion over 46 hours
48:00	Disconnect pump and flush line (5 ml heparinised saline)
Day 3-14	No treatment

Notes:

- Bolus 5FU is recommended to be given over 5 minutes but may be administered as a 15 or 30 minute infusion where this reflects local practice.
- Because of a potential in vitro chemical reaction between Oxaliplatin and chloride ions, care is taken to avoid contact with normal saline in the drip-tubing etc.
- Oxaliplatin may cause vein pain, which is helped by applying an electric heat pad over the vein throughout the 2-hour infusion. Suitable therapeutic heat pads are available from Winterwarm® (38x30cm, model HP5/LT) or Dimplex® (38x28cm) each costing under £20. If this fails, extending the infusion time to 4-6 hours may be helpful.
- Do not use injection equipment containing aluminium.
- The use of pre-packed 'minibags' of 5FU is acceptable.
- Please check with the UoSCTU if your local policy for pre-chemotherapy medication differs to that stated here to confirm if it is acceptable for use in the trial.

Oral antiemetics (starting day 2):

- Dexamethasone 4 mg tds x 1 day; 4 mg bd x 1 day; 4 mg od x 1 day.
- Domperidone or metoclopramide prn.

Note on the use of dexamethasone

- For patients at high risk of steroid side effects (e.g. diabetics) or for those who develop toxicity attributable to steroids (e.g. dyspepsia; dysphoria; etc), the oral steroid should be omitted.

Scheduled tests

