0:00-2:00	Cetuximab 500 mg/m ² IV infusion, 0.5-2 hours (see below) Flush line with 0.9% saline
2:00-3:00	Observe for delayed hypersensitivity reaction
3:00	Flush line with 5% DDextrose
3:00-5:00	L -folinic acid (175 mg flat dose) or d,l -folinic acid (350 mg flat dose) IV infusion, 2 hrs, 250 ml 5% Dextrose Concurrently with:
3.00-5:00	Oxaliplatin 85 mg/m ² IV infusion, 2 hrs, 250 ml 5% Dextrose
5:00	Flush line with 5% DDextrose
5:00-5:05	5-Fluorouracil 400 mg/m ² IV bolus over 5 minutes
5:05-51:00	5-Fluorouracil 2400 mg/m ² IV infusion over 46 hours
51:00	Disconnect pump and flush line (5 ml heparinised saline)
Day 4-14	No treatment

Notes:

- The 1st dose of Cetuximab (500 mg/m²) should be administered by i.v. infusion **over 120 minutes**. There must be at least one hour between completion of Cetuximab and the start of chemotherapy.
- The 2nd dose of Cetuximab (500 mg/m²) should be administered by i.v. infusion **over 90 minutes**. There must be at least one hour between completion of Cetuximab and the start of chemotherapy.

- **Subsequent doses** of Cetuximab (500 mg/m²) should be administered by i.v. infusion **over 60 minutes**. There must be at least one hour between completion of Cetuximab and the start of chemotherapy.
- Bolus 5FU is recommended to be given over 5 minutes but may be administered as a 15 or 30 minute infusion where this reflects local practice.
- Because of a potential in vitro chemical reaction between Oxaliplatin and chloride ions, care is taken to avoid contact with normal saline in the drip-tubing etc.
- Oxaliplatin may cause vein pain, which is helped by applying an electric heat pad over the vein throughout the 2-hour infusion. Suitable therapeutic heat pads are available from Winterwarm® (38x30cm, model HP5/LT) or Dimplex® (38x28cm) each costing under £20. If this fails extending the infusion time to 4-6 hours may be helpful.
- Do not use injection equipment containing aluminium.
- The use of pre-packed 'minibags' of 5FU is acceptable.
- Please check with the UoSCTU if your local policy for pre-chemotherapy medication differs to that stated here to confirm if it is acceptable for use in the trial.

Oral antiemetics (starting day 2):

- Dexamethasone 4 mg tds x1 day; 4 mg bd x1 day; 4 mg od x1 day.
- Domperidone or Metoclopramide prn.

Note on the use of dexamethasone

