- For patients at high risk of steroid side effects (e.g. diabetics) or for those who develop toxicity attributable to steroids (e.g. dyspepsia; dysphoria; etc), the oral steroid should be omitted.

Scheduled tests

- FBC and clinical assessment (NCI toxicity scores) should be performed on the day of starting each cycle (or within 3 working days before) and the results available before starting.
- Biochemistry (including creatinine, bilirubin, magnesium and either AST or ALT) is done at the same time as FBC.
- If patient is clinically jaundiced bilirubin level must be reviewed prior to administration of Oxaliplatin.
- If patient has symptoms of possible hypomagnesemia, check magnesium level and correct as advised (see Appendix XIII).

Toxicity and dose adjustments for OxMdG plus Cetuximab

Allergic/hypersensitivity reactions - Cetuximab

- Severe grade 3/4 hypersensitivity reactions have occurred in 2.2% of patients treated with Cetuximab. One death from angio-oedema has been reported.

- Signs include rapid onset of airway obstruction, urticaria and/or hypotension. 80% occur during or within one hour of the first infusion, but reactions can occur with later infusions.
- **Cetuximab must be administered under the supervision of a physician experienced in the use of antineoplastic medicinal products. Close monitoring is required during the infusion and for at least 1 hour after the end of the infusion. Availability of resuscitation equipment must be ensured.**
- Treatment depends on the grade or severity of the reaction, as follows:

CTC Grade Allergic/hypersensitivity reaction	Treatment
Grade 1 Transient flushing or rash, drug fever <38°C	Decrease the Cetuximab infusion rate by 50% and monitor closely for any worsening. The total infusion time for Cetuximab should not exceed 240 minutes (4 hours).
Grade 2 Rash; flushing; urticaria; dyspnea; drug fever ≥ 38°C	Stop Cetuximab infusion. Administer bronchodilators, oxygen etc. as medically indicated. Resume infusion at 50% of previous rate once allergic/hypersensitivity reaction has resolved or decreased to grade 1 in severity, and monitor closely for any worsening.

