Grade 3 or Grade 4 Grade 3: Symptomatic bronchospasm, with or without urticaria; parenteral medication(s) indicated; allergy-related oedema/angioedema; hypotension Grade 4: Anaphylaxis	Stop Cetuximab infusion immediately and disconnect infusion tubing from the patient. Administer adrenaline, bronchodilators, antihistamines, glucocorticoids, intravenous fluids, vasopressor agents, oxygen etc., as medically indicated. Patients have to be withdrawn immediately from treatment and must not receive any further Cetuximab treatment.

- Once the infusion rate has been slowed for an allergic reaction, it should remain at the slower rate for all subsequent infusions.
- If the patient has a second allergic/hypersensitivity reaction on the slower infusion rate, the infusion should be stopped and no further Cetuximab administered.

- If a patient receives a grade 3 or 4 allergic/hypersensitivity reaction at any time, Cetuximab must be discontinued, but remaining chemotherapy treatment should be continued as normal.
- If there is any doubt whether a reaction is an allergic/hypersensitivity reaction of Grades 1-4, the trial principal co-investigator [name] should be contacted immediately to discuss and grade the reaction.

Skin toxicity - Cetuximab

[figure not shown]
- The acneiform skin rash associated with Cetuximab occurs in over 70% of patients. About 12% have grade ≥ 3 reactions. On longer-term therapy, paronychia occurs in about 10% of patients and can be painful.
- Discussion with a local dermatologist prior to study initiation would be helpful to agree local plans of management and mechanisms for rapid referral in case of severe skin toxicity.
- The occurrence of the rash has been correlated with an increased likelihood of response to treatment, though this information needs to be used with caution, as it is not a direct correlation.
- The rash usually occurs on the face, upper chest and back with multiple follicles and pustules. The onset is usually within the first 3 weeks of treatment and many cases improve by 12 weeks on treatment.

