- Dose modifications for grade 3 toxicity are summarised on the algorithm below. For CTC grade 1 or 2: continue treatment with Cetuximab. If a patient experiences grade 3 skin toxicity (rash effects $> 50\%$ of body surface area), Cetuximab therapy may be delayed for up to 14 days without changing the dose level. If grade 3 skin toxicity occurs for a second and third time, Cetuximab therapy may again be delayed for up to 14 days with concomitant dose reductions to 400 mg/m^2 and then 300 mg/m^2 . Cetuximab dose reductions are permanent. Patients must discontinue Cetuximab if more than 2 consecutive infusions are withheld or grade 3 skin toxicity occurs for a fourth time despite appropriate dose reduction. If the toxicity resolves to grade 2 or less by the following treatment period, treatment may be resumed.
- The investigator should also consider concomitant treatment with topical and oral antibiotics. Grade 1 acneiform eruption: consider treatment with topical antibiotics (e.g. Topical Metronidazole or Erythromycin). Systemic antibiotics (e.g. a second generation tetracycline such as Doxycycline 100mg po daily) should be considered for grade 2 acneiform eruption, and are mandatory for grade ≥ 3 reactions. The threshold for referral to the dermatology clinic should be planned locally but all patients with grade ≥ 3 reactions and probably all with grade 2 reactions should be referred for advice and management. If pruritus occurs an oral antihistamine is advised. Dry skin often occurs (and may contribute to pruritus) general advice on replacing soap with oil for washing, avoidance of hot water for baths or showers and use of emollient creams are beneficial; topical corticosteroids can be used according to local practice. Fissures may occur in dry skin and topical dressings (e.g. hydrocolloid dressings and as advised by your dermatologist) are helpful.

- Colloidal oatmeal preparations (Aveeno, Nature's Gate) can be effective if applied at least 3 times daily⁴⁸. These are available at chemists or on the internet.

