- As above, first calculate the patient's surface area accurately to 2 decimal places, then calculate the exact target dose.
 - *For example, the patient of 1.59m² receiving Cetuximab with the OxMdG regimen without dose-adjustment would have a target dose of $500 \times 1.59 = 795$ mg*
- Then round the Cetuximab dose to the nearest 5 mg.
 - *So the patient in the above example would receive 795 mg Cetuximab.*
- Note that overweight patients are dosed using 1.15 x ideal body weight (see Appendix II) for all chemotherapy drugs. Cetuximab doses should not however be capped to 1.15 x ideal body weight, **please** dose according to the patients actual body weight.

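### The OxMdG plus cetuximab schedule table allows a cetuximab infusion as short as 0.5 hours, but the notes it points to allow nothing shorter than 1 hour (minor)

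*Protocol*

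**What the plan says.** Appendix I of the Protocol sets out the cetuximab regimens. In the day 1 table for cetuximab plus OxMdG, the row for cetuximab 500 mg/m² occupies the 0:00–2:00 slot and gives the time as "IV infusion, 0.5-2 hours (see below").

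The notes under that table give one time per dose, each stated for 500 mg/m²: 120 minutes for the first, 90 minutes for the second, and for all subsequent doses the drug "should be administered by i.v. infusion over 60 minutes". The paragraph above the table also puts the initial infusion at 2 hours.

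The parallel section for cetuximab plus IrMdG shows 2 hours in its table and repeats 120, 90 and 60 minutes in its notes.

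At the head of the appendix, sites are told: "Investigators may find it helpful to copy the relevant schedule from this Appendix", to be kept with the patient's notes.

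**The concern.** The table and its own notes disagree about the shortest permitted infusion. The notes span 1 to 2 hours; the table spans 0.5 to 2 hours. This is dosing text, not background, and infusion rate is one of the protocol's controls on hypersensitivity reactions: for grade 1 the instruction is "Decrease the Cetuximab infusion rate by 50% and monitor closely for any worsening", and for grade 2 it is "Resume infusion at 50% of previous rate once allergic/hypersensitivity reaction has resolved" or fallen to grade 1. A table that sites are encouraged to copy should not show a rate faster than any the protocol intends. What is at stake is the correctness of an administration instruction in Arm B, not any statistical property of the trial.

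**Working it through.** **Inputs (Protocol, Appendices I and II, and section 9.b)**
- Table cell, OxMdG plus cetuximab: 0.5–2 hours, for 500 mg/m².
- Notes to that table, and notes to the IrMdG plus cetuximab table: 120, 90 and 60 minutes, for 500 mg/m².
- Permitted dose reductions for skin toxicity or hypomagnesaemia: "concomitant dose reductions to 400 mg/m^2 and then 300 mg/m^2".
- Worked example in Appendix II, for a surface area of 1.59 m²: "So the patient in the above example would receive 795 mg Cetuximab".
- Duration: 12 weeks before and 12 weeks after surgery, in 14-day cycles.

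**Step 1. Reproduce the stated range.** The shortest and longest of 120, 90 and 60 minutes are 60 and 120 minutes, that is 1–2 hours. The upper limit of 2 hours reproduces. The lower limit of 0.5 hours does not; it is half the shortest time in the notes.

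**Step 2. Look for another source of 30 minutes.**
- *Reaction rules.* These halve the rate, so they only lengthen the infusion, and for grade 1 the total is capped at 240 minutes. The change is also lasting: "Once the infusion rate has been slowed for an allergic reaction, it should remain at the slower rate for all subsequent infusions".
- *Dose reductions.* The 60-minute rate is 500/60 = 8.33 mg/m²/min. At that rate 400 mg/m² takes 400/8.33 = 48 minutes and 300 mg/m² takes 300/8.33 = 36 minutes. Neither is 30, and the cell is for 500 mg/m² in any case.
- *Other drugs.* The 30-minute infusions in these regimens are irinotecan and, as a local option, the bolus 5FU. Neither is cetuximab.
- *IrMdG plus cetuximab table.* It gives 2 hours, with no shorter limit.

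No source is left.

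**Step 3. Size of the discrepancy.**

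| Time for 500 mg/m² | Rate (mg/m²/min) |
|---|---|
| 120 min (dose 1) | 500/120 = 4.17 |
| 90 min (dose 2) | 500/90 = 5.56 |
| 60 min (later doses) | 500/60 = 8.33 |
| 30 min (table's lower limit) | 500/30 = 16.67 |

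Ratio to the fastest intended rate: 16.67/8.33 = 2.0. For the 795 mg example: 795/60 = 13.25 mg/min against 795/30 = 26.5 mg/min.

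**Step 4. Doses that could be affected.** Planned doses: (12/2) × 2 = 12. The lead paragraph fixes the first at 2 hours independently of the notes. The 90-minute rule for dose 2 and the 60-minute rule for later doses stand only in the notes. So if the notes are not read, 12 − 1 = 11 doses are exposed; if they are read, none is.

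**The case against.** The best defence is that the document resolves the conflict itself. The cell sends the reader to the notes, which are explicit and give one time for each dose. A bare range cannot be followed without them, since it does not say which dose gets which time. The row's clock slot runs for 2 hours, so the table schedules no 30-minute infusion. Nothing suggests that a site would copy the table and leave its notes behind. The amendment list also records a change on 8 December 2010 to correct an error in the infusion rates of later cetuximab doses, so sites had been alerted to the subject.

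Most of this stands, and it is why the point is minor. It does not make the cell right: a pointer to notes whose minimum is 60 minutes cannot justify a stated minimum of 30. The amendment entry suggests that 0.5 hours may be a leftover from before that correction, but this is an inference and the point does not need it. The table and the notes are both current text.

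A reader might go further and infer that the slip defeats the reaction rule: halving the rate of a 30-minute infusion gives 60 minutes, merely the ordinary time for later doses. That requires a site to pass over the cross-reference, choose the extreme of the range, and then meet a first grade 1–2 reaction at such a dose. Even then, only the remainder of the infusion in progress is slowed. The protocol says that 80% of reactions occur during or within an hour of the first infusion, which is fixed at 2 hours, and it requires close monitoring throughout and for an hour afterwards. The scenario is speculative and the point does not rest on it.

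**Conclusion.** The lower limit of 0.5 hours is wrong as written and should be 1 hour. It implies a rate twice the fastest one intended (16.7 against 8.3 mg/m²/min at 500 mg/m²). The exposure is conditional: none if the notes are read, and up to 11 of 12 planned doses if the table is used alone. That count assumes full planned treatment in both periods and that the lead paragraph is still followed for dose 1.

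The documents do not show that any site used 30 minutes, or that 30 minutes would cause harm, and neither should be inferred. There is no effect on the endpoint, sample size, power or analysis. Severity: minor.

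**What to change.** In the OxMdG plus cetuximab table, change the infusion time to: 1–2 hours (120 min dose 1, 90 min dose 2, 60 min thereafter; see below). For consistency, the same wording could go into the IrMdG plus cetuximab table, which shows only the dose 1 time, and into the lead paragraphs of both sections; this is optional.

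The cost is the wording of one cell, with no change to design, sample size or analysis. Section 14 expected recruitment to finish at the end of December 2012. If dosing is complete, a file note or a correction to the document of record is enough.
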